### Statistical Analysis Plan

Data will be stored in the Research Electronic Data Capture (REDCap) program on a HIPAA-compliant server with secure access for approved study staff. Analyses will be conducted using SPSS and Supermix. For Aim 2a, I will calculate averages of acceptability ratings, number of sessions completed (retention to treatment), and prescribed strategies documented (compliance). These data will be used to derive expected usage rates for a future trial. For Aim 2b, I will assess the effect of each component on changes in weight and binge eating across time (baseline, post-intervention, follow-up), which will be done by comparing combinations of participants across conditions (see C.5 Research Design). Analyses will be conducted using intent-to-treat linear (for weight) or Poisson (for binge eating) mixed effects models, accounting for data collected at multiple assessment time points nested within individual participants. For each component, I will test differences in change in outcomes across time, with baseline values as the reference. Thus, effects will be modeled as component x time interactions. Cohen's d will be calculated by dividing the mixed effects model derived intervention effect estimate by the pooled standard deviation of the outcome. I also will report results disaggregated by sex and test sex as a moderator to evaluate sex differences in outcomes, which will inform the need for any sex-specific approaches in an optimized intervention. For Aim 3, exploratory analyses using linear mixed models will be performed to test two-way interactions between components on changes in weight and binge eating (e.g., Component 1 x Component 2 x time). Interaction tests are to determine if a set of components impact the overall effect and thus should be retained together in the optimized intervention.

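### The Poisson model for binge counts does not name its random effects or allow for extra-Poisson variation, so its standard errors can be too small

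*SAP*

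**What the plan says.** For Aim 2b the SAP commits to a model type for each outcome: "Analyses will be conducted using intent-to-treat linear (for weight) or Poisson (for binge eating) mixed effects models". The clustering is described as "accounting for data collected at multiple assessment time points nested within individual participants". Three times are analysed: baseline, post-intervention and follow-up. The tested effect is component x time: "For each component, I will test differences in change in outcomes across time, with baseline values as the reference". The SAP will also "test sex as a moderator to evaluate sex differences in outcomes", "which will inform the need for any sex-specific approaches in an optimized intervention".

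Protocol section 8.0 gives the outcome as a count of binge episodes over a 28-day window. No mean, variance or dispersion is given. The only anchor is the entry rule in section 1.0, at least 12 episodes in 3 months.

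Neither document mentions overdispersion, a negative binomial model, a visit-level effect, robust variance or a dispersion check. The SAP does not say whether the participant effect is an intercept alone or an intercept with a time effect.

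**The concern.** A Poisson mixed model sets the variance of a count, given the participant's random effects, equal to its mean. A random intercept lets some people binge more than others at every visit, and that part does no harm. It does not cover the same person having an unusually heavy or light month for reasons outside the model. That variation enters the estimated change over time but not its standard error.

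Component x time and its sex interaction are within-person contrasts, so they are the effects exposed. If the condition holds, p-values for binge eating are too small and intervals too narrow. The sex result has a stated use in designing the optimized intervention. The estimates also feed the planned R01, where false precision, or no dispersion estimate at all, would hinder sizing a trial on a count outcome.

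**Working it through.** **The plan's own figure.** Protocol section 3.0 gives a detectable d of 0.67 with 36 per group, 80% power and two-sided 5% alpha. A noncentral t with 70 df gives 80.05% power, so it reproduces. It concerns a difference in means and does not bear on the count model.

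**Inputs.** From the documents: up to 96 participants, hence 48 per component level if balanced, and three analysed visits. Everything else is assumed:
- Mean counts at baseline/16 weeks/follow-up of 4/2/2, 8/4/4 and 14/6/6. The entry minimum is 12 x 28/91 = 3.7 per 28 days.
- Person SD of 0.6 on the log scale.
- Visit-level log-variance v of 0 to 0.4.
- 75% women for the sex test.
- No true effect and no dropout.

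**What v means.** Within-person variance/mean = 1 + mean x (exp(v) - 1). For v = 0.05 to 0.2 at baseline this is 1.21 to 1.89 (mean 4), 1.41 to 2.77 (mean 8) and 1.72 to 4.10 (mean 14).

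**Closed-form check, baseline versus 16 weeks.** With n people per level and means m0 and m1, the log rate ratio within a level is log(ΣY1/ΣY0).
- Poisson variance: (1/n)(1/m0 + 1/m1).
- True variance: (1/n)[1/m0 + 1/m1 + 2(exp(v) - 1)K], with K = exp(0.6²) = 1.433.
- True SE/model SE: r = √[1 + 2(exp(v) - 1)K/(1/m0 + 1/m1)]. Here n cancels.
- Rejection rate: 2Φ(-1.96/r).

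Example, means 8 and 4, v = 0.1: 2 x 0.1052 x 1.433 = 0.3015 and 1/8 + 1/4 = 0.375. So r = √1.804 = 1.343, and 2Φ(-1.459) is about 14%.

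**Comparison with fitted models.** Rejection (%) of a nominal 5% component x 16-week test, Poisson with random intercept, maximum likelihood, 2,000 runs per cell:

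| Means | Method | v=0 | 0.05 | 0.1 | 0.2 | 0.4 |
|---|---|---|---|---|---|---|
| 4/2/2 | formula | 5 | 7 | 10 | 15 | 25 |
| 4/2/2 | fitted | 5.8 | 6.3 | 9.0 | 15.1 | 24.0 |
| 8/4/4 | formula | 5 | 10 | 14 | 23 | 37 |
| 8/4/4 | fitted | 5.8 | 8.8 | 13.3 | 22.6 | 35.4 |
| 14/6/6 | formula | 5 | 12 | 19 | 31 | 46 |
| 14/6/6 | fitted | 4.3 | 13.0 | 19.2 | 29.7 | 45.4 |

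At v = 0.4 the visit-level SD (0.63) exceeds the person SD, so that column is an outer bound.

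**Different noise model.** Gamma visit noise, means 12/5/5, person log-SD 0.5, 400 runs: 4.3% at v = 0, 17% at 0.1, 29% at 0.25 and 40% at 0.5 (here v is the gamma variance).

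**Sex moderator.** Intercept only, 36 women and 12 men per level, v = 0.05 to 0.2: 7.5 to 14.9% (4/2/2), 10.0 to 21.8% (8/4/4) and 11.8 to 30.0% (14/6/6). At v = 0: 4.2 to 5.7%.

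**Adding a random linear slope to the Poisson model.** Over the settings run with v above 0, up to 0.4, component x time rejects 6 to 24% at 16 weeks. At follow-up it stays near nominal (3 to 7% over all runs). The sex test rejects 9 to 23% at 16 weeks and 3 to 7% at follow-up.

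**Remedies under the same kind of noise.**
- Negative binomial with random intercept, sex test: 5 to 8%.
- Poisson with a visit-level effect, component test: 4 to 6% in seven of eight settings and 9% in one (300 runs).
- Participant-clustered robust standard errors: 3.8 to 6.8% (400 runs). In 20,000 runs of the two-visit contrast above, 5.4 to 6.8%.

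**The case against.** Several stronger readings are tempting, and the documents do not support them.

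- *That the SAP fits no random effects.* A mixed model with visits nested in participants implies a participant effect. What is missing is which one. The inflation above occurs with an intercept already fitted.
- *That every binge-eating test would be too liberal.* With a random slope, follow-up contrasts are close to nominal and the inflation is mainly at 16 weeks. Without extra within-person variation nothing is inflated.
- *That components would be chosen on false positives.* Protocol section 3.0 bases retention on effect sizes and says the pilot was not sized for formal tests. The SAP's effect size does not use the model standard error: "Cohen's d will be calculated by dividing the mixed effects model derived intervention effect estimate by the pooled standard deviation of the outcome". No significance threshold is set for the sex result, which also includes separate reporting by sex.
- *That the linear model in Aim 3 is part of the same fault.* There the SAP says "exploratory analyses using linear mixed models will be performed to test two-way interactions between components on changes in weight and binge eating". Additive and multiplicative interactions are different questions, and a change of scale does not by itself invalidate a test. It is a separate, exploratory matter.

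Two further cautions stand. The rejection rates come from assumed inputs and show sensitivity, not what this trial will see. The SAP also points elsewhere ("see C.5 Research Design") to a section not among the supplied documents. It is cited for how conditions are compared, but it could state the random effects.

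What survives is that tests and intervals are planned on a model that is safe only if there is little within-person extra variation, and the plan has no step to detect it.

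**Conclusion.** The point holds in a conditional form. If 28-day counts vary within person beyond Poisson, standard errors for component x time and for the sex moderator can be too small. Under the assumed inputs, an intercept-only nominal 5% test at 16 weeks rejects about 6 to 30% of the time for component x time, and 8 to 30% for sex, when v is 0.05 to 0.2. With v = 0 it is about 5%. The direction follows from the model. The size depends on means, person SD, v and sex split that the documents do not give.

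The consequence is minor to moderate: it touches the planned tests and the precision attached to pilot estimates, not the effect-size basis for keeping a component. It is worth changing because the remedy is cheap and uses data already collected.

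**What to change.** In Aim 2b, name the random effects and replace the plain Poisson model for binge eating with one of these:
- a negative binomial mixed model (log link) with a participant random intercept;
- Poisson with a participant intercept and an observation-level random effect;
- Poisson with a participant intercept and participant-clustered robust standard errors.

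Report the dispersion estimate for R01 planning; under the robust option it must be estimated separately. The SAP names SPSS and Supermix, so confirm that the chosen option can be fitted there. If the section cited as C.5 already states the random effects, copy them into the SAP.

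A random time effect is optional, since three visits support it poorly. With a slope truly present, 7 to 8% of negative binomial slope fits had a parameter at its bound. If one is included, write down a fallback. The price of leaving it out is that an intercept-only negative binomial test rejected about 9% at follow-up when people's time trends differed.

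The cost is a sentence or two of SAP text and one more parameter. If counts are truly Poisson, intervals widen by about 1 to 2%: for the sex test at 8/4/4, mean SE 0.0751 against 0.0738, a ratio of 1.018. The negative binomial sex test can stay slightly liberal, up to 8%, with 12 men per component level.

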STUDY TITLE:

Testing Intervention Strategies for Addressing Obesity and Binge Eating

PRINCIPAL INVESTIGATOR:

[name]

Department of Medical Social Sciences

VERSION DATE:

February 14, 2022

Indicate Vulnerable Population(s) to be Enrolled	 Children  Cognitively Impaired Adults  Pregnant Women (IF the research activities will affect the pregnancy or the fetus)  Prisoners (or other detained/paroled individuals)
International Research (check this box if you will collect data from individuals located outside the United States)	
Research involving external collaborators (some research activities will be carried out by individuals not employed by Northwestern or NU affiliates)	
Research has U.S. Federal government funding (e.g., NIH, NSF, other federal agencies/departments)	

1.0 Purpose of the study:

The purpose of this study is to design a mobile intervention that targets obesity and binge eating. Two studies will be conducted with adults with obesity (BMI ≥ 30) and recurrent binge eating (≥ 12 binge episodes in the past 3 months). The first study will employ a user-centered design approach to design a 16-session guided self-help, mobile intervention and conduct usability testing to inform intervention refinements prior to a pilot trial. The second study will involve a randomized pilot trial that will determine the feasibility of delivering the intervention protocol and generate preliminary data on the effect of the intervention on changes in weight and binge eating at 16 weeks (post-intervention) and 3 months post-intervention (follow-up). Additional design sessions (as part of Study 1) will be conducted with adolescents (ages 13-17 years) with elevated weight status (BMI $\geq 75^{\text{th}}$ percentile for age and sex) and who endorse loss of control eating or overeating (≥ 3 loss of control and/or overeating episodes in the past 3 months). The specific aims and hypotheses of this research are to:

Aim 1: Employ a user-centered design approach to design a mobile intervention that targets obesity and binge eating and conduct usability testing to inform intervention refinements prior to the pilot trial.

Hypothesis 1: Quantitative and qualitative data from usability testing will inform intervention refinements prior to the pilot.

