Aim 2: Conduct a randomized pilot trial of the mobile intervention that targets obesity and binge eating, using a 2^3 full factorial design, to (2a) determine the feasibility of delivering the intervention, and (2b) derive estimates of the effect of 3 intervention components on changes in weight and binge eating at post-intervention and follow-up to inform a future R01 trial.

Hypothesis 2: Feasibility will be based on study recruitment and retention rates, acceptability, retention to treatment, and compliance documenting prescribed strategies. Effect sizes estimates will be used to power a R01 trial.

Exploratory Aim 3: Explore if intervention components interact to change weight and binge eating at post-intervention and follow-up.

Hypothesis 3: The factorial design will enable me to test if the effect of a component is moderated by another component, to ensure the optimized intervention retains components that directly or indirectly impact outcomes.

Background / Literature Review / Rationale for the study:

Obesity affects one third of US adults.¹ Obesity is associated with medical and psychosocial morbidities, impaired quality of life, increased mortality, and high health care costs.²⁻⁸ Up to 30% of treatment-seeking adults with obesity engage in binge eating,⁹⁻¹¹ an eating disorder behavior characterized by eating a large

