Study 2 Randomized Pilot Trial: Up to 96 participants will be enrolled into the trial. The pilot trial was not powered for hypothesis testing, as the goal of the pilot is to inform a R01 trial of an optimized intervention. This goal will be achieved by evaluating feasibility and generating effect sizes of each component on changes in outcomes.³⁹⁻⁴¹ The effect sizes will inform which components to retain in the optimized intervention and be used to power a subsequent trial. However, a power calculation was run to determine the effect size this pilot trial will be powered to detect. Using intent-to-treat analyses with $n=36/\text{group}$ for tests of each component (Aim 2b), assuming 80% power, 5%

alpha, and a two-sided test, there is power to detect main effects of $d=0.67$. This effect is in the range of past trials of digital BWL and CBT.^{26-29,42-47} It is acknowledged that this is a large effect; however, because the primary purpose of this research is for training and to collect pilot data, increasing the sample size could decrease feasibility and threaten these two goals. As such, a smaller N to maintain appropriate scope was prioritized.

4.0 Recruitment and Screening Methods:

Recruitment Methods, Study 1 Needs Assessment: Participants will be recruited from potentially eligible individuals who have consented on discord to complete screens and be considered for qualitative research projects (i.e., “missions”).

Recruitment Methods, Study 1 Design & Usability Testing (including the Field Trial) and Study 2 Randomized Pilot Trial: Participants will be recruited from clinics at Northwestern University (e.g., Center for Lifestyle Medicine) and the University of Chicago (e.g., Eating Disorders Program, Center for Surgical Treatment of Obesity) and the community via flyers, media (including online social media such as Facebook, Instagram, Reddit, and Craigslist), newsletters, referrals, and word of mouth. We also will recruit participants using ResearchMatch and The New Normal, which are free participant recruitment online platforms that are accessible to researchers at participating institutions including Northwestern University, and Northwestern’s StudyTracker. Across all recruitment method platforms, information/study advertising content will remain consistent with IRB-approved recruitment language.

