Coaching: Each participant will be assigned a coach, trained and supervised weekly by a licensed clinical psychologist. Coaching follows a low-intensity model aimed at encouraging participants to use the intervention and practice skills in their daily lives, as well as provide some technical support as needed. Coaches will use messaging such as text or e-mail to communicate with participants through a password-protected website on a secure server. Coaching will begin with an initial ~30-minute phone call to establish goals and build rapport, ensure the participant can access the intervention, and set expectations for the coach-participant relationship. Thereafter, participants will receive ~1-2 messages per week from their coach to offer encouragement, reinforce app use, and check-in on progress or challenges. Coaches also will aim to respond to participant-initiated messages within 1 working business day. An optional ~10-minute call at week 8 (mid-way through the intervention) will be offered to participants to check in on their progress.

Study assessments will occur at the following intervals: baseline, mid-intervention (5-weeks and 10-weeks), post-intervention (16 weeks) and follow-up (3-months post-intervention). Baseline, post-intervention, and follow-up assessments will include interviews and questionnaires; mid-treatment assessments will only include questionnaires. Interviews and questionnaires will assess the following topics: personal and demographic information, treatment utilization, height, weight, number of binge episodes over the past 28 days, eating-related, cognitions, behaviors, and impairment, food security, eating and physical activity behaviors, social support for diet and exercise, mood, and experiences with technology. Intervention use data (from start of

intervention through 3-month follow-up) also will be automatically collected. Study procedures will be conducted remotely during remote work requirements. Upon return to work, participants and researchers will have the option conduct these activities remotely or in-person.

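### The SAP's single Cohen's d formula, applied as written to the Poisson model for binge eating, divides a log rate ratio by an SD in episodes and does not give a standardised effect

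*SAP*

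**What the plan says.** For Aim 2b the SAP plans "intent-to-treat linear (for weight) or Poisson (for binge eating) mixed effects models" and states that "effects will be modeled as component x time interactions", with baseline as the reference. It then defines the effect size once, without distinguishing the two outcomes: Cohen's "d will be calculated by dividing the mixed effects model derived intervention effect estimate by the pooled standard deviation of the outcome". Neither document names the link function, describes a back-transformation to episode counts, or names a rate ratio as the effect measure for binge eating.

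The binge-eating outcome is a count. Protocol section 8.0 (Study 2 assessments) lists the "number of binge episodes over the past 28 days".

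The effect sizes have a declared use. Protocol section 3.0 says: "The effect sizes will inform which components to retain in the optimized intervention and be used to power a subsequent trial". Hypothesis 2 in section 1.0 says: "Effect sizes estimates will be used to power a R01 trial".

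**The concern.** Cohen's d needs a numerator and a denominator in the same unit, so that the unit cancels. For weight they match: a linear-model interaction is a difference in change in weight, and the SD is in weight units. For binge eating they do not. A Poisson mixed model with its standard log link gives an interaction coefficient that is a log ratio of rates and has no unit. Dividing it by an SD in episodes per 28 days leaves a quantity in units of 1/episodes.

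The pilot exists to produce these effect sizes. A binge-eating d of the wrong size could not be compared with the weight d, or with the detectable d of 0.67 quoted in Protocol section 3.0. An R01 sample size taken from it would be wrong.

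**Working it through.** **The plan's own figure.** Protocol section 3.0 gives 36 per group, 80% power, two-sided 5% alpha and a detectable d of 0.67. A two-sample t-test gives a detectable d of 0.6696 at 36 per group, and power of 0.80 at d = 0.67. The figure reproduces, and it is a d for a difference in means.

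**Inputs.** The model type, the interaction as the effect and the d formula come from the SAP; the 28-day count comes from Protocol section 8.0. The log link and the use of the untransformed coefficient are assumptions. The documents give no post-treatment mean, SD or rate ratio, so these are assumed too. The only anchor is the entry criterion in section 1.0, at least 12 "binge episodes in the past 3 months": if evenly spread, 12 × 28/91 = 3.7 per 28 days.

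**Formulas.** Let m0 and m1 be the mean counts with the component off and on, with equal baseline means, and let RR = m1/m0.

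- d as the SAP writes it: ln(RR)/SD
- d on the count scale: (m1 − m0)/SD
- count-scale d divided by the SAP's d: (m0 − m1)/ln(m0/m1)

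The SD cancels, so the factor depends only on the means. Required n is approximately proportional to 1/d², so n based on the SAP's d is about the square of the factor times the n needed.

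**Results at RR = 0.6** (ln(1/0.6) = 0.5108):

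| m0 | m0 − m1 | Factor | n from the SAP's d ÷ n needed |
|---|---|---|---|
| 5 | 2.00 | 3.92 | 15.3 |
| 3.7 | 1.48 | 2.90 | 8.4 |
| 2 | 0.80 | 1.57 | 2.5 |
| 1 | 0.40 | 0.78 | 0.61 |

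**Where the direction reverses.** The factor equals 1 when m0 = −ln(RR)/(1 − RR). That is 1.39, 1.28, 1.19 and 1.12 episodes for RR of 0.5, 0.6, 0.7 and 0.8. Above that mean the SAP's d is too small and n too large; below it the reverse holds.

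**Illustration in sample size.** With m0 = 5, RR = 0.6 and SD = 5, the SAP's d is −0.5108/5 = −0.10 and the count-scale d is −2/5 = −0.40. A two-sample t-test at 80% power and two-sided 5% alpha needs 1,505 per group for the first and 100 for the second.

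**A check that needs no mean count.** A standardised effect should not change when the same data are expressed per week. The SAP's quotient does: with RR = 0.6, an SD of 5 per 28 days gives −0.10, and the same SD per week (5/4 = 1.25) gives −0.5108/1.25 = −0.41.

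**Comparison with the plan's benchmark.** At SD = 5, a value of 0.67 on the SAP's formula would require RR = exp(−0.67 × 5) = 0.035, a 96.5% reduction in rate.

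**The case against.** The strongest reply is that the SAP never says the numerator is the raw coefficient. A model-derived effect estimate could be a difference in predicted episode counts, and a denominator on the outcome scale points that way. On that reading d is valid and the fault is one missing clause. This reading is possible, but the SAP does not state it. The same paragraph identifies the effect with the interaction term and applies one formula to both models, so an analyst who followed the text would divide the coefficient.

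The size is assumed, and this stands. The figure of 3.7 is a baseline floor, whereas the factor depends on component-off means after treatment. Every participant receives the weight-loss content and is offered coaching, and half of those without a given component receive each of the others, so these means may be well below baseline. Baseline may equally be well above the floor. At a mean of 1.5 and RR 0.6 the factor is only 0.6/0.5108 = 1.17 (n about 1.4 times), and near 1 the direction reverses.

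The documents also do not say how the R01 would be powered or what it would compare. The step from d to n above is therefore conditional, and an implausible d might be noticed before use, although the SAP contains no such check. Finally, the SAP refers to a section C.5 that was not available for this review. It is cited for how conditions are combined, so a definition of d there is unlikely but cannot be excluded.

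**Conclusion.** The formula is wrong as written for binge eating and should be fixed. Under the standard log link and the untransformed interaction, it yields a number that depends on the time unit of the count and is not Cohen's d. Across assumed component-off means of 1 to 5 and RR 0.6, the correct value is 0.78 to 3.9 times the SAP's value, and an n based on the SAP's d would be 0.61 to 15.3 times what is needed. Even the direction depends on post-treatment means that the documents do not give; 1,505 versus 100 is an illustration and not a forecast.

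The consequence is limited in three ways. The component-by-time test does not use d. The ranking of components within binge eating is largely preserved. The d for weight has numerator and denominator on one scale. What is affected is the absolute size of the binge-eating effect, its comparison with weight, and any sample size derived from it.

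**What to change.** In the Aim 2b text of the SAP:

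1. State the link function of the Poisson model.
2. Say that the present d formula applies to weight only.
3. For binge eating, report the component-by-time rate ratio with its 95% CI as the effect size, and power the R01 from the rate ratio, the mean count and the overdispersion.
4. If a d for binge eating is still wanted, define it as the between-level difference in change in marginal, back-transformed mean counts predicted by the model, divided by the pooled SD of counts at a named time point.

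If predicted counts were intended all along, item 4 alone settles the scale of d. The cost is SAP wording: no new data are needed and the fitted model does not change.

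### For binge eating, Aim 3 names linear mixed models for component interactions where Aim 2b uses Poisson models, without a reason, so main effects and interactions may be read on different scales

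*SAP*

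**What the plan says.** The SAP is a single paragraph. For Aim 2b it assigns models by outcome: "intent-to-treat linear (for weight) or Poisson (for binge eating) mixed effects models". Each component's effect is its interaction with time. Later in the same paragraph, for Aim 3, "exploratory analyses using linear mixed models will be performed to test two-way interactions between components on changes in weight and binge eating"; the term tested is component by component by time. No reason is given for naming only linear models, no transformation of the counts is mentioned, and no link function is stated for the Poisson model.

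Protocol section 8.0 (Study 2 assessments) has the study assessments record the "number of binge episodes over the past 28 days", so binge eating is an episode count. Exploratory Aim 3 in Protocol section 1.0 names no model, so nothing there resolves the difference.

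Both analyses serve one decision. Protocol section 3.0 says of the component effects: "The effect sizes will inform which components to retain in the optimized intervention and be used to power a subsequent trial". The SAP says of Aim 3: "Interaction tests are to determine if a set of components impact the overall effect and thus should be retained together in the optimized intervention". Hypothesis 3 in Protocol section 1.0 gives the purpose of testing moderation as "to ensure the optimized intervention retains components that directly or indirectly impact outcomes".

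**The concern.** The paragraph uses linear as the alternative to Poisson in Aim 2b, then names only linear in Aim 3 for both outcomes. An analyst who follows the text would fit a Gaussian model to binge counts for the interactions and a Poisson model to the same counts for the main effects. With the usual log link, the main effect is then a ratio of rates and the interaction a difference of differences in episodes.

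Interaction depends on the scale of measurement more than most quantities do. If each component multiplies the rate by a constant, there is no interaction on the log scale but there is one in episodes. If each removes a fixed number of episodes, the reverse holds. The same data could therefore suggest that two components work against each other, act independently or reinforce each other, depending on the model. The plan does not say which scale governs when components are chosen for the optimized intervention.

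**Working it through.** **1. The plan's own figure.** Protocol section 3.0 states a detectable main effect of d = 0.67 with 36 per group, 80% power and two-sided 5% alpha. A two-sample t-test gives power 80.05% at d = 0.67 and a minimum detectable d of 0.6696. The figure reproduces. It concerns Aim 2b main effects and does not depend on the Aim 3 model.

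**2. Inputs.** The documents give no expected binge counts or component effects, so the values below are assumptions. The one anchor is the entry criterion of at least 12 episodes in 3 months, which is 12 × 28/91 = 3.7 per 28 days. Baselines of 4, 8 and 14 per 28 days were used, halved when neither component is given, so the post-intervention mean m is 2, 4 or 7. The third component is taken to have no effect. Baseline means are equal across cells and cancel.

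**3. Multiplicative effects.** Each component has rate ratio r, so the cell means are m, mr, mr and mr².
- Log-scale interaction: ln(m × mr² / (mr × mr)) = 0.
- Linear interaction: m − 2mr + mr² = m(1 − r)².
- Linear main effect (size of reduction, averaged over the other component): m(1 − r²)/2.
- Ratio of the last two: 2(1 − r)/(1 + r).

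| r | Ratio | Linear interaction, m = 2 | Linear interaction, m = 7 |
|---|---|---|---|
| 0.8 | 0.4/1.8 = 22% | 0.08 episodes | 0.28 episodes |
| 0.7 | 0.6/1.7 = 35% | 0.18 | 0.63 |
| 0.6 | 0.8/1.6 = 50% | 0.32 | 1.12 |

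**4. Additive effects with the same single-component cuts.** The cell means are m, ma, ma and m(2a − 1).
- Linear interaction: m − 2ma + m(2a − 1) = 0.
- Ratio of rate ratios: (2a − 1)/a² = 0.6/0.64 = 0.94 at a = 0.8; 0.4/0.49 = 0.82 at a = 0.7; 0.2/0.36 = 0.56 at a = 0.6.

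The two models test different null hypotheses.

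**5. Size against sampling error.** Simulation used 8,000 runs per setting, 24 or 18 people per cell of the 2×2 (N = 96, the enrolment ceiling, or N = 72, which is 2 × 36), person-level log-SD 0.5 or 0.8, and dispersion 0 or 0.2. It used two time points, as a simplification of the planned three.
- Linear test, no component effects: rejects in 4.2 to 5.1% (N = 96) and 4.3 to 5.1% (N = 72).
- Linear test, additive effects (its own null): 3.9 to 5.6% and 4.0 to 5.7%.
- Linear test, multiplicative effects: the interaction in step 3 is 0.04 to 0.39 standard errors (N = 96) or 0.03 to 0.37 (N = 72), and the test rejects in 4.2 to 6.7% and 4.4 to 6.7%.
- As an illustration of scale dependence only, a log-link test with robust standard errors under additive effects at N = 96 rejects in 5.4 to 7.4% (a = 0.8), 7.2 to 14.9% (a = 0.7) and 18.2 to 62.0% (a = 0.6). The top of that range needs baseline 14, no extra dispersion and a combined cut of 80%; with dispersion 0.2 at that baseline it is 31 to 33%.

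**6. Would a plain Poisson replacement behave?** With no component effects and model-based standard errors, the Poisson interaction test rejects in about 4 to 6% at dispersion 0 but about 12 to 34% at dispersion 0.2. With robust standard errors it is about 5 to 8%. These runs also use a two-time-point stand-in for the mixed model.

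**The case against.** The strongest reply is that linear in Aim 3 is loose shorthand for the models already assigned in Aim 2b. That is possible in so short a plan, and it is why the point is conditional on a literal reading. The two readings still give different analyses, and the text does not choose between them.

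A second reply is that the linear analysis does little harm. This largely stands. A reader might infer that fitting a linear model to counts inflates the false-positive rate of the interaction test; step 5 does not support that. Nor are the rejections under multiplicative effects errors: an interaction in episodes is then real, and the test simply has little power to see it. An additive interaction is a legitimate target and can be reported beside rate-ratio main effects, provided the scale is stated.

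A reader might also take the 18 to 62% as an error rate of the plan. It is not: it describes a log-link test under additive effects, whereas the linear test named in Aim 3 stays near 5% there.

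Finally, one might extend the point to Cohen's d. The SAP defines d within Aim 2b, where binge eating has only a Poisson model, so no conflicting linear-model d is planned. How d is obtained from a Poisson model is a separate question and adds no weight here.

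The objection that a bare switch to Poisson could make matters worse also stands, by step 6, and it shapes the fix.

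**Conclusion.** The inconsistency is in the text and nothing else in the documents reconciles it. That it produces a mismatch of scales rests on two assumptions: that Aim 3 means what it literally says, and that the Aim 2b Poisson model uses a log link. Given those, the binge-eating interaction that is absent on one scale is present on the other, at 22 to 50% of the linear main effect, or a ratio of rate ratios of 0.94 to 0.56, for assumed single-component cuts of 20 to 40%. At the smaller effects the difference would be invisible at this sample size.

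The consequence is modest and confined to how the binge-eating interaction is interpreted when components are retained. Aim 3 is exploratory, the pilot was not sized for formal tests, the linear test's false-positive rate is not materially affected, weight is untouched, and the stated d = 0.67 does not change. It should be fixed because the interaction results are given a role in a decision and the correction is small.

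**What to change.** In Aim 3, restrict linear mixed models to weight. For binge eating, test component by component by time in the same count mixed model and link as Aim 2b, and name the link. Handle overdispersion in both aims, by robust standard errors, an observation-level random effect or a negative binomial model. Report the ratio of rate ratios with its 95% confidence interval, together with model-predicted mean counts for each cell, so that additive effects can be read from the same fit.

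If an interaction in episodes is what is wanted, say so and give the reason.

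The cost is two or three sentences in the SAP. A count model is already planned for Aim 2b, and no new data or participants are needed.
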